### **3.4 Randomization**

This study is observational and no randomization of subjects will occur.

### **3.5 Blinding**

This study is observational and no blinding will occur.

### **3.6 Missing Data**

The primary analysis will be based on the data as observed. Two additional sensitivity analyses will be performed where subjects with missing data are (1) assumed to have no cardiopulmonary events and (2) assumed to have a cardiopulmonary event.

### **3.7 Sample Size**

Approximately 760 subjects are planned to be enrolled in the study to provide 634 subjects in the final analysis.

When the sample size is 634, the logistic regression test of  $\beta=0$  ( $\alpha = 0.050$  two-sided) will have 80% power to detect a  $\beta$  of 0.747 (an odds ratio of 2.111); this assumes that one normally distributed covariate  $x$  is being added to the model after adjustment for prior covariates, that its multiple correlation with covariates already in the model is 0.500 and, that the proportion of successes at the mean of  $x$  is 0.050.

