A novel algorithm for determining risk of acute cardiac complications, including cardiac arrest, for patients presenting to the ED has recently been reported. Unlike prior risk stratification tools that relied on basic vital sign data, this algorithm utilizes multiple metrics of heart rate variability (HRV) as well as a machine learning approach to solve the risk classification problem. The algorithm requires the collection of vital sign data, patient mental status, and *at least* 5 minutes of continuous electrocardiography (to calculate HRV metrics). It was shown to be more accurate than MEWS in predicting cardiac arrest within 72 hours of admission to hospital. Furthermore, the algorithm has been used to predict serious complications (mortality, cardiac arrest, ventricular tachycardia, hypotension requiring inotropes or intra-aortic balloon pump (IABP) insertion, intubation or mechanical ventilation, complete heart block, bradycardia requiring pacing, and recurrent ischemia requiring revascularization) within 72 hours in patients presenting to the ED with chest pain. In this patient population, a score of 4 or higher from the algorithm had a sensitivity of 0.880, specificity of 0.680, positive predictive value of 0.195, and a negative predictive value of 0.985 which was better than using ST elevation/depression and troponin in predicting complications within 72 hours. The primary limitation of the algorithm is that it has been developed and tested in Singaporean patients. Verification of the results of the studies using this algorithm in other patient cohorts is required. As such, the proposed study will investigate the sensitivity and specificity of the algorithm.

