#### **2.1.4 *Study Objectives***

##### **2.1.4.1 *Primary Objective***

The primary objective is to verify an existing prediction algorithm of cardiopulmonary events.

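### The 80% power in Section 3.7 is power against no association for one unnamed covariate; it does not bear on the algorithm's accuracy, and Section 3.2 plans no sensitivity, specificity or intervals to fill the gap.

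*Combined protocol and SAP*

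**What the plan says.** Section 2.1.4.1 gives the aim: "The primary objective is to verify an existing prediction algorithm of cardiopulmonary events". Section 3.1 repeats it. Section 1.1 explains that the algorithm has so far been developed and tested only in Singaporean patients, and that "the proposed study will investigate the sensitivity and specificity of the algorithm". The same section reports the accuracy found earlier in chest-pain patients at a score of 4 or higher: sensitivity 0.880, specificity 0.680, PPV 0.195 and NPV 0.985.

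The only power statement is in Section 3.7: "When the sample size is 634, the logistic regression test of" a zero coefficient, two-sided at 0.05, "will have 80% power to detect a" coefficient of 0.747, which is an odds ratio of 2.111. The covariate x is not named. It is normally distributed and "is being added to the model after adjustment for prior covariates". The section assumes "that its multiple correlation with covariates already in the model is 0.500" and an event proportion of 0.050 at the mean of x.

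Section 3.2 plans a binary logistic regression on explanatory variables that are not listed, followed by a ROC curve and its AUC. It gives no score cut-off, no sensitivity or specificity at a cut-off, no interval for the AUC, and no statement of what result would count as verification. The only confidence intervals in Section 3.1 are those around the means of continuous variables.

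**The concern.** A zero slope means that the covariate carries no information about events once the other covariates are in the model. Rejecting it shows some association. It does not show that the algorithm separates patients as well in a new population as it did in the old one, which is the reason Section 1.1 gives for the study. A score that has lost much of its accuracy can still have a slope clearly different from zero.

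The 80% figure therefore answers a question other than the one in the objective, and nothing else in the plan says how well 634 subjects can answer the objective's own question. For sensitivity the relevant count is the number of subjects with an event, which is a small fraction of 634. At the end of the study there would be a regression, an AUC without a stated interval, and no planned figure to set beside the earlier sensitivity and specificity.

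**Working it through.** **1. The plan's own figure.** Inputs from Section 3.7: b = 0.747, p = 0.050, two-sided alpha 0.05 (z = 1.960), power 80% (z = 0.842). The Hsieh (1989) formula for one normal covariate is

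n = [1.960 + exp(−b²/4) × 0.842]² × (1 + 2pd) / (p b²) / (1 − R²), with d = [1 + (1 + b²) exp(5b²/4)] / [1 + exp(−b²/4)].

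Here b² = 0.558, exp(−b²/4) = 0.870, d = 2.209 and 1 + 2pd = 1.221. The squared bracket is 7.247. So 7.247 × 1.221 / 0.0279 = 317.1, and dividing by 1 − 0.50 gives 634.2. The 634 and the 80% reproduce, and exp(0.747) = 2.111.

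The match needs 0.500 to be R², whereas the text calls it a multiple correlation. With R² = 0.25 the same inputs give 423, power at 634 is about 94%, and the detectable odds ratio is about 1.83. That is a separate matter: it changes the power against no association, not the question tested.

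**2. What the powered slope could mean for accuracy (illustration only).** Assume that x is the algorithm score, that b is per SD, and that the prior covariates have no effect on the outcome.
- Equal-variance normal approximation: AUC = Φ(0.747/√2) = 0.70; sensitivity at specificity 0.68 = Φ(0.747 − 0.468) = 0.61.
- Directly under the logistic model with 5% at the mean of x: AUC 0.698, sensitivity 0.60.
- Sensitivity reported in Section 1.1 at the same specificity: 0.880.

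Relaxing the last assumption moves the answer. Keep the adjusted slope at 0.747 and R² at 0.5, and give a composite of the prior covariates its own slope (assumed values). The unadjusted AUC of x becomes:

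| Slope of composite | AUC of x |
|---|---|
| 0 | 0.70 |
| 0.3 | 0.74 |
| 0.5 | 0.77 |
| 1.0 | 0.81 |

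**3. Expected events among 634.**
- 5% throughout: 0.05 × 634 = 31.7, about 32.
- 5% at the mean of x with b = 0.747: averaging the model over a standard normal x gives 6.25%, and 0.0625 × 634 = 39.6, about 40.
- Prevalence implied by Section 1.1: PPV(1 − spec) / [sens(1 − PPV) + PPV(1 − spec)] = 0.0624 / (0.7084 + 0.0624) = 8.1%, about 51 events. Check: NPV = 0.68 × 0.919 / (0.68 × 0.919 + 0.12 × 0.081) = 0.985, as stated there.

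**4. Precision at those counts.** Exact (Clopper-Pearson) 95% intervals for an observed sensitivity near 0.88:

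| Events | Observed | Exact 95% CI |
|---|---|---|
| 32 | 28/32 | 0.71-0.96 |
| 40 | 35/40 | 0.73-0.96 |
| 51 | 45/51 | 0.76-0.96 |

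The lower side is 12 to 17 points wide. A symmetric normal half-width, 1.96 × √(0.88 × 0.12/n), is 9 to 11 points and understates it. For specificity 0.68 with 583 to 602 non-events, 1.96 × √(0.68 × 0.32/n) is about 0.037 to 0.038, or about 4 points.

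**5. Power for a sensitivity floor.** The documents state no floor, so every floor here is an assumption. Exact test, one-sided 2.5%, true sensitivity 0.88:

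| Assumed floor | 32 events | 40 events | 51 events |
|---|---|---|---|
| 0.65 | 82% | 90% | 96% |
| 0.70 | 66% | 80% | 85% |
| 0.75 | 24% | 47% | 59% |
| 0.80 | 9% | 13% | 25% |

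The 80% in Section 3.7 cannot be carried over to sensitivity without choosing a floor.

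**The case against.** The strongest reply is that Section 3.7 claims no more than it delivers. It names its test, the Protocol Summary gives the primary analysis as regression, and the power statement matches that method. Section 3.2 also plans an AUC, so discrimination will be estimated. This stands as far as it goes: the power statement is accurate for its own test, and accuracy is not ignored. But the AUC has no planned interval or benchmark, it belongs to a fitted model whose variables are not named, and sensitivity and specificity at the score cut-off are absent.

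Some stronger readings are tempting, and the documents do not support them.
- *A significant slope will be taken as verification.* A reader might infer this because it is the only test that is powered. No section says so, and no success criterion of any kind is set.
- *The study's stated purpose is to confirm 0.880 and 0.680.* These figures appear only as background. They come from chest-pain patients, a narrower group than Section 2.2.2 admits. Their outcome list also differs: it includes mortality, which the primary list in Section 3.2 does not name separately.
- *An algorithm far worse than the published one has 80% power to reach the powered result.* This depends on x being the score and on the prior covariates having no effect. The score's AUC could be higher, as the table above shows, or lower. If x is some other variable, the power statement says still less about the algorithm.
- *The study is underpowered for sensitivity.* That depends wholly on a floor that the plan does not set.

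**Conclusion.** The point holds in limited form. The 80% is power to reject no association for one unnamed covariate. It does not address the aim of verifying the algorithm and investigating its sensitivity and specificity, and Section 3.2 does not supply the missing accuracy analysis. This follows from the text alone and needs no conversion of the slope.

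The sizes are conditional. AUC about 0.70 and sensitivity about 0.60 at specificity 0.68 illustrate the gap under the three assumptions in step 2. The precision figures assume 5% to 8.1% of subjects with an event and an observed sensitivity near 0.88; the exact interval then reaches down to between 0.71 and 0.76. It would go too far to say that 634 subjects are too few, or that the plan equates a significant slope with success. The change should be made, but it alters neither recruitment nor data collection.

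**What to change.** Keep 760 enrolled and 634 analysed.

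**Section 3.2.** Add the sensitivity and specificity of the existing score at the published cut-off (4 or higher), each with an exact 95% CI, and a 95% CI for the AUC of the score itself. State that the verification conclusion rests on these estimates and intervals, including the lower limits, and not on the significance of a regression coefficient. Report them beside 0.880 and 0.680, noting that the benchmark comes from chest-pain patients with a somewhat different outcome list. State also that an interval merely containing 0.880 does not prove verification.

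**Section 3.7.** Label the 80% as power against no association only. Add the expected events (about 32 to 51), the exact intervals in step 4, and the specificity half-width of about 4 points. If power for a sensitivity floor is quoted, show it over a range of assumed floors as in step 5, not for one floor.

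**Cost.** One small added analysis on data already collected, no extra subjects, and a precision statement less favourable than 80% power.

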## **4 Monitoring Procedures**

### **4.1 Monitoring**

This study will be monitored according to appropriate regulations and SOPs. The Investigator will allocate adequate time for such monitoring activities. The Investigator will also ensure that the monitor is given access to all the study-related documents and related facilities, and has adequate space to conduct the monitoring visit.

### **4.2 Investigator/Site Selection**

The following documents must be received prior to site initiation and maintained at the site and Sponsor:

- Signed Clinical Study Agreement;
- Current Medical License;
- Current Curriculum Vitae (CV) for Primary Investigator(s) – dated and signed

- IRB/EC Approval Letter; and
- IRB Membership List and/or Accreditation Statement

Additional items that may be collected, are preferably collected prior to initiation, but not required at that time:

- CV's for Co-Investigator(s) – dated and signed; and
- Site Personnel Training Record(s).

#### **4.3 Case Report Form Review**

A database that is compliant with 21 CFR Part 11 will be used. eCRFs received from the site will be documented with their date of receipt and entered into the study database. If there is missing, incomplete, unclear or discrepant information recorded on eCRFs, a Data Clarification Form (DCF) will be generated. The DCF will be sent to the Investigator for completion and signed by the appropriate site personnel. The DCF will then be sent back to the Sponsor to update the database. All common modules are demographics, screening, adverse events, labs, medical history, medications, procedures, treatment discontinuation, study completion, and signatures.

#### **4.4 Source Documents**

Source data is all information, original records of clinical findings, observations, or other activities in a clinical study necessary for the reconstruction and evaluation of the study. Examples of source data include: Patient Medical Records, recorded data from automated instruments, and subject files involved in the clinical study.

#### **4.5 Interim On-site Monitoring**

The monitor will maintain personal contact with the Investigator and staff by fax, phone, mail, and on-site visits. The monitor will require access to all subjects' records at each site visit. These may include:

- Patient Medical Records
- Investigator Administrative Records
- Subject Binders

Monitoring will verify:

- Protocol and regulatory compliance;
- Verification of data recorded on Case Report Forms to source documents; and
- Adequate subject enrollment.

#### **4.6 Final Monitoring Visit**

At the close of the study, the monitor will make a final on-site visit. The purpose of this visit is to:

- Collect all outstanding study data;

- Insure that the Investigator's files are accurate and complete;
- Review record retention requirements with the Investigator;
- Assure that all requirements are met for the closure of the study.

## 5 Study Administration

### 5.1 Study Sponsor

ZOLL Medical is the study sponsor and responsible for selecting qualified Investigators and providing them with the information they need to conduct the study properly, ensuring proper monitoring of the clinical site, ensuring that IRB review and approval are obtained, and ensuring that any reviewing IRBs are promptly informed of significant new information about the study.

### 5.2 Applicable Regulations

The following regulations were considered in developing/designing this study and apply to the ongoing conduct of the study:

- ISO 14155

#### 5.2.1 Institutional Review Board

Prior to participating in the study, the Investigator must forward written approval from the appropriate reviewing IRB. The Investigator is responsible for obtaining and maintaining IRB approval to participate in this study and forwarding evidence of IRB notification of approval, disapproval, or study termination to Sponsor.

#### 5.2.2 Informed Consent

Patients will typically be unable to give informed consent at the time of enrollment based on the seriousness of their injuries or the process in which medical care is given. As this is an observational study and the data collected is only that of standard of care treatment this trial should be considered non-significant risk. Every effort will be made to ensure that consent is received from the patient or patient's legally authorized representative (LAR) within 24 hours of patient enrollment.

If a patient or LAR is unwilling or unable to sign Informed Consent the data will be removed from the database and not be considered in the final analysis. These patients not participating will be replaced to ensure that the number of patients approved for this study is met.

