## **1.2 *Risks/Benefits***

### **1.2.1 *Risks***

This is an observational study. The only risk is a breach of the patient's protected health information.

If a patient or LAR is unwilling or unable to sign Informed Consent the data will be removed from the database and not be considered in the final analysis. These patients not participating will be replaced to ensure that the number of patients approved for this study is met.

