#### **2.1.2 *Scope and Duration***

This is a prospective, multi-center, observational study.

Enrollment in this study is expected to take approximately 18 months. Subjects are enrolled upon arrival to the emergency department and followed for 72 hours.

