## 2.3 Study Procedures

Schedule of Events			
Hospital Stay Status	Admit	During	Discharge/ Withdrawal
Inclusion/Exclusion Criteria	X		
Informed Consent	X 		
Study Evaluations			
Demographics (date of birth/age, gender and ethnicity)	X		
Smoking status	X		
ED diagnosis (primary)	X		
Final diagnosis (primary)			X
Medications including beta-blockers, combined alpha and beta-blockers, digitalis, calcium channel blocker, bronchodilators, amiodarone, other anti-arrhythmics	X	X	X

Medical history, specifically a history of ischemic heart disease, diabetes, hypertension, dyslipidemia, stroke, cancer, respiratory disease, renal disease, congestive heart disease, PCI, CABG, MI)	X		
Physical exam [REDACTED]	X		
Glasgow Coma Score (GCS)	X		
Blood labs; specifically troponin and/or CKMB if available	X		
12-lead ECG (if patient is reporting chest pain)	X 		
Continuous 3-lead ECG recording of at least five minutes	X		
Chest Pain	X		
Symptom onset/peak within 24 hours of presentation	X		
Pain score	X		
MEWS Score	X		
Cardiopulmonary events (acute pulmonary edema, lethal arrhythmias, cardiogenic shock, myocardial infarction, percutaneous coronary intervention, coronary artery bypass surgery, recurrent ischemia requiring revascularization)	X	X	X
In-hospital cardiac arrest		X	
In-hospital death		X	
Status changes (admitted to ICU, admitted to ward, etc.)		X	
Length of stay			X
Adverse Events	X	X	X

1 Every effort will be made to ensure that consent is received from the patient or patient's legally authorized representative (LAR) within 24 hours of patient enrollment. If the patient or LAR refuses consent the patient will be withdrawn from the study.

[figure not shown]
2 If applicable

3 Serious adverse events must be reported to the Sponsor within 24 hours of becoming aware of the event, but no later than 10 days after the event.

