### 2.3.1 Subject Enrollment

Subjects are enrolled in this study when they have:

- Met all eligibility criteria.

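### Deleting and replacing enrolled subjects when consent cannot be obtained may lose events selectively; the consent passages do not agree on this group, and no count or bound of the removals is planned.

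*Combined protocol and SAP*

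**What the plan says.** Enrollment depends on eligibility alone. Section 2.3.1 ("Subjects are enrolled in this study when they have") lists no other condition, and section 2.1.2 adds: "Subjects are enrolled upon arrival to the emergency department and followed for 72 hours".

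Consent comes afterwards. Section 5.2.2 expects that "Patients will typically be unable to give informed consent at the time of enrollment based on the seriousness of their injuries" or because of how care is delivered. It promises every effort so that "consent is received from the patient or patient's legally authorized representative (LAR) within 24 hours of patient enrollment".

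Four places then bear on what happens if consent is not obtained:

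- **Section 5.2.2:** "If a patient or LAR is unwilling or unable to sign Informed Consent the data will be removed from the database". Those data are left out of the final analysis.
- **Section 1.2.1:** the same rule, and "These patients not participating will be replaced to ensure that the number of patients approved for this study is met".
- **Section 2.3, Schedule footnote 1:** "If the patient or LAR refuses consent the patient will be withdrawn from the study". It says nothing about inability to sign, or about data already collected.
- **Section 2.5:** examples of withdrawal reasons, with consent not among them.

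Section 5.2.3 also requires the investigator to keep all entered CRF data for each enrolled subject, which sits awkwardly with deletion.

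**The concern.** Whether a subject stays in the data set is settled after enrollment, while outcome events are occurring. Cardiac arrest and intubation are primary events (section 2.1.5) and in-hospital death is a secondary one (section 2.1.6). Each can stop a patient from signing. If no LAR is available, the record goes and the event goes with it.

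Replacement restores the number of subjects but not the lost events, because replacements must themselves have a patient or LAR able to sign. The two extra analyses in section 3.6 reclassify subjects with missing data, and deleted subjects are no longer in the database. As planned, a reader of the results could not tell how many subjects were removed as unable to consent, or why.

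The study aims to verify the algorithm in a new population, and section 1.1 names sensitivity and specificity as what it will investigate. With few events expected, losing a handful matters.

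**Working it through.** **Inputs from the documents.** Section 3.7: 760 enrolled, 634 analysed, beta 0.747, two-sided alpha 0.05, 80% power, correlation term 0.500, event proportion 0.050 at the covariate mean. Section 1.1: published sensitivity 0.880, specificity 0.680 and PPV 0.195 at a score of 4 or higher.

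**Assumptions.** The documents give no removal rates, so I vary them: 5% of non-events and 10% to 50% of events removed. I take 0.050 as the overall event rate. Replacements have the same mix as retained subjects, so 634 is still reached.

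**1. Reproducing the plan's figure.** Hsieh (1989) formula for logistic regression:

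n = [z(0.975) + exp(-b²/4) z(0.80)]² (1 + 2Pd) / (P b²) / (1 - R²), with d = [1 + (1 + b²) exp(5b²/4)] / [1 + exp(-b²/4)].

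Here b² = 0.558, exp(-b²/4) = 0.870 and d = 2.209. So n = 7.247 × 1.221 / 0.0279 / (1 - R²) = 317.1 / (1 - R²).

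- R² = 0.5 gives 634.2, and power at 634 is 0.800. The plan's figure reproduces.
- A multiple correlation of 0.500 read literally (R² = 0.25) gives 423. I use R² = 0.5 below because it matches 634.

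Expected events: 634 × 0.05 = 31.7.

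**2. Removal that depends on outcome only.** If fractions fe of events and fn of non-events are removed, the observed rate is q = 0.05(1 - fe) / [0.05(1 - fe) + 0.95(1 - fn)].

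For fe = 0.20 and fn = 0.05:

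- q = 0.0400 / (0.0400 + 0.9025) = 0.0424.
- Events in 634: 634 × 0.0424 = 26.9.
- PPV = 0.88q / [0.88q + 0.32(1 - q)] = 0.109, against 0.126 at q = 0.05.
- Power, with q in place of P: z = [√(634 × 0.0424 × 0.558 × 0.5 / 1.187) - 1.960] / 0.870 = 0.637, so power is 0.738.

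| Events removed (non-events 5%) | Observed rate | Events in 634 | PPV | Power |
|---|---|---|---|---|
| No removal in either group | 5.00% | 31.7 | 0.126 | 80% |
| 10% | 4.75% | 30.1 | 0.121 | 78% |
| 20% | 4.24% | 26.9 | 0.109 | 74% |
| 30% | 3.73% | 23.7 | 0.096 | 69% |
| 50% | 2.70% | 17.1 | 0.071 | 55% |

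Sensitivity stays at 0.88 in every row. In a logistic model the slopes and AUC are likewise unaffected; the intercept shifts by ln(0.80/0.95) = -0.17 in the 20% case.

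The published accuracy figures imply a prevalence of 8.1%: odds = (0.195/0.805) × (0.32/0.88) = 0.088. There the 20% case takes PPV from 0.195 to 0.169.

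**3. Removal that also depends on the score among events.** In the extreme case every removed event scored 4 or higher, and sensitivity = (0.88 - fe)/(1 - fe). If score-positive events are twice as likely to be removed, sensitivity = 0.88(1 - 2k)/(1 - fe), with k = fe/(2 × 0.88 + 0.12).

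| Events removed | Sensitivity, extreme | Sensitivity, twice as likely |
|---|---|---|
| 10% | 0.867 | 0.874 |
| 20% | 0.850 | 0.866 |
| 30% | 0.829 | 0.856 |
| 50% | 0.760 | 0.824 |

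**4. The opposite direction.** If instead 5% of events and 20% of non-events were removed, q = 0.0475 / (0.0475 + 0.7600) = 5.9% and PPV rises to 0.147. With equal removal in both groups and no dependence on the score, nothing is biased.

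**The case against.** Several counter-arguments have force.

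- **An LAR may sign.** A patient's own incapacity need not lead to removal. The 24 hours is a target; no passage orders removal at that point or bars later consent. A reader might infer that the rule drops the sickest patients because of their outcome. The documents do not establish that: they give no removal rate by outcome, and section 5.2.2 also attributes inability to the care process. Low-risk patients discharged before anyone approaches them would push the bias the other way.
- **The Schedule does not restrict withdrawal to refusers.** One might read footnote 1 as contradicting section 5.2.2. It is silent on inability, and section 2.5 offers its reasons only as possible ones. This is a gap to reconcile, not two opposed rules.
- **Sensitivity is not automatically biased.** Outcome-only removal leaves sensitivity, specificity and AUC alone, and AUC is the planned summary in section 3.2. Bias in sensitivity needs score-related removal among events. That is plausible, since mental status feeds the algorithm (section 1.1) and also affects capacity to sign, but it is not shown. Even the extreme fall of 0.03 at 20% loss is smaller than the standard error with 38 events in 760: √(0.88 × 0.12/38) = 0.053.
- **PPV is not a planned estimate.** It appears only as a published background figure.
- **Some records already exist.** The Subject Discontinuation CRF captures the reason for exit, and enrollment logs are kept.

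All of this limits what can be claimed. It does not answer the core point: the stated rule can remove events selectively, and no planned analysis would show whether it had.

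**Conclusion.** The point holds as a conditional risk. Sections 1.2.1, 2.3 (footnote 1), 2.5 and 5.2.2 do not give one complete rule for subjects who cannot sign. Where such subjects are removed, neither replacement nor section 3.6 recovers what is lost.

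The size and direction of any bias are unknown. Under the assumed 20% and 5% losses, the event rate, PPV and power change by the amounts in the second row of removals in the first table (4.24%, 0.109 and 74%). These figures rest on the assumed removal fractions and on treating the plan's event proportion at the covariate mean as the overall rate. For sensitivity, 0.85 is the extreme of that scenario rather than an expected value.

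This is a low-cost improvement that would make an otherwise invisible bias visible. It does not show that the study's accuracy estimates will be wrong.

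**What to change.** 1. **Reconcile** sections 1.2.1, 2.3 (footnote 1), 2.5 and 5.2.2. Distinguish refusal from inability to sign, and state for each what happens to data already collected. Check the result against the record-keeping requirement in section 5.2.3.
2. **Ask the reviewing IRB** whether minimal de-identified score and outcome data may be kept for subjects who die or remain incapacitated with no LAR. This is the IRB's decision. Section 5.2.2 already describes the data as standard of care and the study as non-significant risk.
3. **In every case, keep and report a de-identified count of removals by reason:** refused, died first, incapacitated with no LAR, discharged before approach.
4. **Add a bounding sensitivity analysis** of event rate, sensitivity and specificity for the m subjects removed as unable. With E events, TP of them score-positive, among n analysed subjects, the event rate lies between E/(n + m) and (E + m)/(n + m). Sensitivity lies between TP/(E + m) and (TP + m)/(E + m). Specificity is bounded in the same way among non-events.

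The cost is protocol wording, one IRB request and a little extra analysis; the Discontinuation CRF and enrollment log already support the count. Without IRB permission the bounds are worst-case only, and wide. For example, with an assumed E = 32, TP = 28 and m = 5, sensitivity is bounded only between 28/37 = 0.76 and 33/37 = 0.89.
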